4. METHODOLOGY

The Brady MX study is a prospective, sequential, post market study with an educational phase and any market released pacemaker from the Medtronic family of devices may be used in this study. It is hypothesized that the use of a practice-specific process improvement intervention consisting of education, diagnostic algorithm(s) and

documentation tools that advocate and reinforce adherence to consensus treatment guidelines will improve the quality of care for patients with sinus node dysfunction (SND). The study will be conducted in two phases, with Phase I serving as control subjects and Phase II measuring the impact of the intervention.

The study will be conducted in compliance with the Clinical Investigation Plan, Clinical Trial Agreement, approved labeling, latest version of the Declaration of Helsinki, and laws and regulations of the country in which the study is conducted, including data protection laws.

Principles of the Declaration of Helsinki have been incorporated into this study by means of the patient informed consent/Patient Data Release process, IRB/MEC approval (if required); study training, clinical trial registration, risk benefit assessment, and publication policy, etc.

The study may enroll up to 500 Mexican subjects. with at least 210 subjects enrolled per study phase. Once enrolled, Phase I subjects should be followed for approximately 6 months and Phase II subjects should be followed for approximately 6 months. Brady MX is anticipated to be completed in mid-2018.

Subject data will be collected at enrollment/baseline, diagnostic assessment visits and implant visit. Data will continue to be collected until one of the exit criteria has been met. Brady MX does not mandate specific requirements regarding any other procedures, subject visits to the clinic, clinical treatment of subjects or device programming. Clinical data will be collected using electronic case report forms.

Centers will be eligible to enroll subjects in Brady MX upon Medtronic's receipt of required center activation materials and written approval.

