4.3. Study Design

There are two phases for Brady MX

Figure 1: IMPROVE Brady Study Design

Phase I: This phase of the study serves as a control period. During Phase I physicians will assess and treat subjects per their site’s standard care practice.

Enrollment for Phase I is anticipated to occur for approximately 6 months but will continue until a minimum of 210 subjects have been enrolled. For subjects enrolled during Phase I, collection of diagnostic assessment and implant data will be complete 6 months after the last enrollment. At that time, all Phase I subjects will be exited

Phase II:
The objective of the Brady MX study is to provide investigators with comprehensive resources that may be adapted by the Principal Investigator and his/her colleagues to create a practice specific process improvement intervention to improve the quality of care for patients.

At the completion of Phase I, the Principal Investigator and co-investigators will complete an educational workshop and be given access to the Brady MX toolkit. In addition, the Principal Investigator and his/her colleagues are encouraged to adapt tools from the Brady MX toolkit to create a practice specific process improvement intervention.

Immediately following completion of the educational workshop, study investigators will receive written authorization from Medtronic that they are authorized to enroll subjects in Phase II. Enrollment during this phase is anticipated to occur for approximately 6 months but will continue until a minimum of 210 subjects have been enrolled.

The Brady MX process improvement intervention toolkit may include an education workshop, diagnostic algorithm(s), patient video and tools for investigators to educate their patients on their disease state, available therapy options, and benefits and risks associated with the therapy options.

For subjects enrolled during Phase II collection of diagnostic assessment data will be complete 6 months after last enrollment. At that time, any subjects without a diagnosis will be exited from the study.

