5.4. Diagnostic Assessment Visit(s)

A diagnostic assessment is any post enrollment visit to the study center for continued diagnostic assessment or management. During these visits information about utilization of diagnostic tests, results and cardiovascular medication use will be collected. Information about the final diagnosis and treatment decision will also be collected during the diagnostic assessment visit. The diagnostic assessment visit data will be complete:

- When the subject meets study exit criteria
- 6 months after the last Phase I enrollment for Phase I subjects
- 6 months after the last Phase II enrollment for Phase II subjects
- Patient education tools have been reviewed with the patient by the investigator (Phase II only)

The study protocol does not dictate when the Diagnostic Assessment(s) is/are to occur.

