11.1. Primary Objective(s)

Primary Objective #1

Evaluate the impact of the intervention on the diagnosis of SND.

Hypothesis

The primary objective will be tested with the following hypothesis:

$$H_0: p_{1t} = p_{2t}$$

$$H_A: p_{1t} \neq p_{2t}$$

where p_{1t} is the proportion of patients with SND in Phase I and p_{2t} is the proportion of patients with SND in Phase II at time point t .

Endpoint Definition

The absolute change in the proportion of subjects diagnosed with SND at pre-specified time points ($\% = \text{number diagnosed} / \text{number enrolled} \times 100$ at time point $t = 6$, or t is a multiple of 6 representing any additional 6-month interval for which there is sufficient follow-up information) and the absolute change in the number of subjects diagnosed with SND per person-year.

Analysis Methods

A. Statistical Methodology

To compare the proportion of subjects with an SND diagnosis pre-intervention (Phase I) to the proportion post-intervention (Phase II), a binomial exact test will determine statistical significance. The proportion of subjects diagnosed will be evaluated at multiple time points because the time to diagnosis is expected to vary by hospital. Thus, times are pre-specified starting at 6 months and any additional 6-month interval thereafter for which there is sufficient follow-up data available to compare study phases. Proportions calculated at all available time points will be reported. Additionally a Poisson regression will compare the average number of subjects with an SND diagnosis in Phase I and Phase II where the subject time in study is treated as an offset in the model. The above described tests will be performed separately within site as well as overall.

B. Determination of Patients/Data for Analysis

All subjects that are enrolled in the study and that meet study inclusion/exclusion criteria will be included in the determination of the proportion estimates. The proportion estimates will be calculated based on information from fixed time points at 6 months of follow-up, and any additional 6-month interval thereafter for which there is sufficient follow-up data available to compare study phases. The number of subjects that obtain a SND diagnosis by pre-specified time point t is included in the numerator and the number of subjects enrolled is included in the denominator.

Sample Size Methods and Assumptions

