The proportion of SND diagnoses in subjects with bradycardia is currently unknown. The power calculations conservatively assume that the SND diagnosis will be 10% at six months of follow-up, or equivalently an SND incidence of 0.2 diagnoses per person-year. If 200 subjects are collected each in Phase I and in Phase II, assuming a type I error of 0.05 and power of 0.80, a binomial exact test will detect an increase in SND diagnosis of at least 10%. For example, the study will find a statistically significant difference between a Phase I SND percentage of 10% at 6 months and a Phase II SND percentage of 20% at 6 months. If the proportion of SND diagnoses is smaller than 10%, there will be more power to detect significant differences in the diagnosis proportion. It is expected that the study attrition rate may be 5% of the study population. To account for attrition, the sample size for Phase I will be a minimum of 210 subjects and for Phase II will be a minimum of 210 subjects.

Primary Objective #2

Evaluate the impact of the intervention on SND subjects receiving a referral for an indicated IPG device.

Hypothesis

The primary objective will be tested with the following hypothesis:

$$H_0: p_{1t} = p_{2t}$$

$$H_A: p_{1t} \neq p_{2t}$$

where p_{1t} is the proportion of patients referred for an IPG in Phase I and p_{2t} is the proportion of patients in Phase II at time point t .

Endpoint Definition

The absolute change in the proportion of subjects receiving therapy referral for an indicated IPG at pre-specified time points ($\% = \text{number receiving IPG}/\text{number with SND diagnosis} \times 100$ at time point t where $t = 3, 6$, and any additional 3-month interval for which there is sufficient follow-up information) and the absolute change in the number of subjects implanted per person-year.

Analysis Methods

Statistical Methodology

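### Does the loosely defined person-time behind the per-person-year comparison for Primary Objective #1 distort the comparison between phases?

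*Combined protocol and SAP*

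**What the plan says.** Section 11.1 gives Primary Objective #1 a two-part endpoint. The first part is the change in the proportion of enrolled subjects diagnosed with SND at 6 months and at later multiples of 6 months. The second is "the absolute change in the number of subjects diagnosed with SND per person-year". The hypotheses are stated for the proportions and tested with a binomial exact test. The rate comparison is introduced as an addition: a Poisson regression "where the subject time in study is treated as an offset in the model".

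The sample-size paragraph of the same section assumes a diagnosis share of "10% at six months of follow-up, or equivalently an SND incidence of 0.2 diagnoses per person-year".

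Follow-up is described in two ways:

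- Section 4: "Phase I subjects should be followed for approximately 6 months and Phase II subjects should be followed for approximately 6 months".
- Section 4.3, Phase I: "collection of diagnostic assessment and implant data will be complete 6 months after the last enrollment". Section 5.4 closes diagnostic data "6 months after the last Phase I enrollment for Phase I subjects" and "6 months after the last Phase II enrollment for Phase II subjects".

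Enrollment length is open at the upper end: "Enrollment for Phase I is anticipated to occur for approximately 6 months but will continue until a minimum of 210 subjects have been enrolled". Section 4.3 says the same of Phase II. Section 5.6 allows, but does not require, a subject without a pacing indication to leave early.

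**The concern.** A rate needs a clock with a start and a stop. For this objective the plan names the clock but does not say whether it stops at diagnosis or at a common horizon. For Primary Objective #2 it does give the start, at SND diagnosis. With 6 months of uniform enrollment, the two descriptions of follow-up give either about 6 months per subject or 6 to 12 months.

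If one phase accumulated more person-time than the other, the same share diagnosed would produce different rates. The reported change per person-year could then be non-zero with no change in the share diagnosed, and could disagree with the 6-month proportion. Since the rate is listed in the definition of a primary endpoint, that would be awkward to interpret.

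**Working it through.** **Inputs from the plan.** 10% diagnosed at 6 months, 0.2 per person-year and 200 subjects per phase (Section 11.1); about 6 months of enrollment per phase and data to 6 months after the last enrollment (Section 4.3); 26 months in total (Section 1.2).

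**Assumptions.** Uniform enrollment and 10% SND in both phases. In the simulations (10,000 trials per scenario), diagnosis falls at 0.5 to 6 months unless stated, and SND subjects leave 1 month after diagnosis. The test is a Wald test on the log rate ratio with SE = √(1/d₁ + 1/d₂), where d₁ and d₂ are the numbers diagnosed. This is equivalent to Poisson regression with a log-time offset.

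**1. The plan's own figure.** Rate = share / years = 0.10/0.5 = 0.20 per person-year. It reproduces.

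**2. Does 0.2 contradict the longer follow-up?** Mean follow-up would be (6 + 12)/2 = 9 months = 0.75 year.

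- If no diagnosis occurs after month 6, the rate is 20/150 = 0.133 when time runs to the data cut, or 20/140.4 = 0.142 when it stops at diagnosis.
- If diagnoses continue at a constant rate, the hazard is −ln(0.9)/0.5 = 0.211. About 29 of 200 are diagnosed by the cut, and 29/150 gives 0.19 (time to the cut) against 0.21 (time to diagnosis).

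So 0.2 fits the longer follow-up under a constant rate. Section 11.1 itself plans later time points because time to diagnosis varies between hospitals.

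**3. Do the two follow-up lengths separate the phases?** Each is written for both phases. At 6 against 6 months the rates are 0.20 and 0.20; at 9 against 9 months they are 0.133 and 0.133. The ratio is 1.00 either way.

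**4. Unequal enrollment.** Mean follow-up to the cut is L/2 + 6 months for an enrollment period of L months. The baseline timeline is 6 + 6 + 6 + 6 = 24 months, so the longest extension of one phase within 26 months is 8 + 6 + 6 + 6 = 26, which leaves no gap for the workshop.

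- Mean follow-up is then 10 against 9 months, a ratio of 10/9 = 1.11. Simulated person-years are 157.1 and 142.1, ratio 1.11, rejection 6%.
- Hand check: with about 20 diagnoses per phase, SE = √(1/20 + 1/20) = 0.316, and ln(1.11)/0.316 = 0.33 standard errors.
- With diagnoses spread over 12 months the ratio is 1.01. At a constant rate it is 1.00 (4%).
- Enrollment of 12 against 6 months gives 1.32 (14%) but needs 12 + 6 + 6 + 6 = 30 months.

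**5. Unequal early exit.** Suppose non-SND subjects leave at a mean of 6 months in Phase I and 3 months in Phase II. The documents give neither the share nor the timing.

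| Share leaving early | Person-years, Phase I / Phase II | Rate ratio | Rejection |
|---|---|---|---|
| 100% | 76.1 / 49.5 | 1.54 | 27% |
| 75% | 92.6 / 72.7 | 1.28 | 11% |
| 50% | 109.2 / 95.7 | 1.14 | 6–7% |
| 25% | not tabulated | 1.06 | 5% |

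Reversing the first row gives 0.65 (26%). With everyone leaving early at 6 against 5 months, the ratio is 1.11 (5.5%).

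**6. How much does the stop rule matter?** With 6 months of follow-up, stopping at diagnosis moves a 10% phase from 0.200 to between 0.203 and 0.218, and a 20% phase from 0.400 to between 0.414 and 0.480 (mean time to diagnosis 5 down to 1 months). With a mean of 3 months in both phases, the planned contrast is 0.444/0.211 = 2.11 instead of 0.400/0.200 = 2.00.

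**7. The primary test.** Its denominator is the number enrolled at a fixed time point. The sample size comes from 10% against 20%: a two-sided normal approximation at 0.05 and 80% power gives 199 per phase, against the stated 200. Person-time enters neither.

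**The case for a change.** The strongest case for a change is that part of a primary endpoint cannot be computed in a single pre-specified way. Exit is discretionary, enrollment length is open, and the Phase II toolkit may include diagnostic algorithms, so equal timing of negative work-ups cannot be taken for granted. Section 4.3 also exits everyone at the end of Phase I but names only undiagnosed subjects at the end of Phase II. A short definition would cost little.

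Part of this stands: the stop rule is unwritten and the follow-up wording is loose. The rest is weaker.

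- The clock is largely inferable. Sections 4.2 and 5.3 date enrollment at consent, and Section 5.6 lists the exits. The start at diagnosis for Objective #2 reads as the stated exception.
- The end-of-phase wording matters only if time after diagnosis is counted. If 20 diagnosed Phase II subjects each stayed 6 months longer (an assumption), 150 person-years would become 150 + 20 × 0.5 = 160, and the ratio 150/160 = 0.94. Stopping at diagnosis removes this.
- A rate and a proportion are different quantities. If the intervention shortens the work-up, a higher rate per year observed reflects a real change in process, so the 27% is not a false-positive rate for the rate hypothesis.
- The exit reason concerns a pacing indication, whereas the scenarios in step 5 treat it as absence of SND. Table 1 records final diagnosis and device indication separately.
- A full repair has its own cost. Capping at 6 months alone still leaves 1.41 (18%) in the most extreme case. Reaching 1.00 means crediting subjects who have left with time up to month 6, when nobody was observing them. Both phases then have 95.4 person-years, and the rate, 20/95.4 = 0.21, nearly restates the 6-month proportion.

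**Conclusion.** No change follows. The two descriptions of follow-up apply equally to both phases and create no difference between them. With unequal enrollment inside the stated study duration, the ratio is at most about 1.11 with 6% rejection, and 1.00 at a constant diagnosis rate. Rejection above about 10% requires either enrollment lengths that overrun the 26 months, or most non-SND subjects leaving early with clearly different timing between phases; no document figure supports the latter. These results assume 200 subjects and 10% SND in each phase, with uniform enrollment.

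The remaining gap is one that analysts fill sensibly: count time from consent to the earliest of SND diagnosis, exit or data cut, by the same rule in both phases, and read the result as a rate among those still under observation. Whether subjects who have left should be credited with further time is a trade-off on which statisticians reasonably differ. The hypotheses, the exact test, the sample size and the study's main conclusion are the same under any of these choices.

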1.2. Study Scope

The study may be conducted in up to 10 sites under oversight by the “Secretaria de Salud” in Mexico. The study will be conducted in two phases, with Phase I serving as control subjects and Phase II measuring the impact of the intervention. Up to 500 subjects will be enrolled in the study with at least 210 enrolled per phase. An enrollment target of 45 subjects per center in total is desired to make center-specific outcomes more meaningful and reliable in measuring changes in diagnostic rates and patient acceptance of indicated therapy. Centers that enroll faster than others will be allowed to enroll up to 42 subjects within each phase of the study.

All study subjects will be followed until the study exit criteria are met or until official study closure. Study closure is defined as closure of a clinical study that occurs when Medtronic and/or regulatory requirements have been satisfied per the Clinical Investigation Plan and/or by a decision by Medtronic or regulatory authority, whichever occurs first. The expected study duration from first enrollment to last follow-up, is approximately 26 months.

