4.4. Minimization of Bias

Potential sources of bias in this study may result from the Hawthorne effect, selection of study centers, selection of subjects, treatment of subjects, and evaluation of study data. The following methods have been incorporated into the study to minimize potential bias.

- Center selection criteria, documented under separate cover, will need to be met prior to participation in Brady MX. Study center characteristics will be collected at activation on possible differences that may affect the primary endpoints. Centers will be used as their own control
- Subjects will be screened to confirm eligibility with the help of screening logs, for enrollment with defined inclusion/exclusion criteria prior to enrollment
- Subject demographics will be collected at baseline on possible differences that may affect the primary endpoints
- It is anticipated that the distribution of subjects with various co-morbidities will vary by study centers. To minimize potential bias, all sites will be encouraged to enroll at least 5 subjects in each study Phase and enrollment at a site cannot exceed 42 subjects per phase to ensure a more even distribution of data
- All study Clinicians will be required to follow the Clinical Investigation Plan
- All study clinicians and Medtronic personnel will be trained on their respective aspects of the clinical investigation plan using standardized training materials.

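### The overall test for Primary Objective #1 is not stratified by site, so a systematic change in site mix between phases would bias it; stratifying is a cheap improvement

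*Combined protocol and SAP*

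**What the plan says.** Section 11.1 (Primary Objective #1, Statistical Methodology) compares the proportion diagnosed with SND in Phase I and Phase II, and "a binomial exact test will determine statistical significance". A Poisson regression with time in study as an offset supports it. Then: "The above described tests will be performed separately within site as well as overall". No stratified test, site term or combined within-site estimate is specified.

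Section 4.4 lists as a safeguard against bias: "Centers will be used as their own control". The plan also expects sites to differ. Section 4.4 says "It is anticipated that the distribution of subjects with various co-morbidities will vary by study centers", and Section 11.1 says "the time to diagnosis is expected to vary by hospital".

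Site enrollment is bounded but not fixed. Section 4.4 has a soft lower limit ("all sites will be encouraged to enroll at least 5 subjects in each study Phase") together with a firm upper one ("enrollment at a site cannot exceed 42 subjects per phase"). Section 1.2 adds: "Centers that enroll faster than others will be allowed to enroll up to 42 subjects within each phase of the study". It also states a desired total of 45 subjects per center. Under Section 4.3 each phase enrolls until at least 210 subjects are in, and Section 10.2 allows a center to be closed for lack of enrollment.

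**The concern.** Two layers of analysis are planned. The per-site tests respect the own-control principle but are too small to support a conclusion. The overall test has the sample size but compares totals, so it reflects both the change within sites and any change in which sites supplied the subjects.

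If sites with higher diagnosis rates contribute a larger share in Phase II, the pooled difference overstates the intervention. If they contribute a smaller share, part of a real effect is lost, in a study sized for 80% power with little margin. Two conditions are needed: site diagnosis rates that differ, and a change in site shares that tracks those rates. The plan makes the first plausible and leaves room for the second, but nowhere says that the second will happen.

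**Working it through.** **The plan's own figure.** Section 11.1 gives 10% versus 20%, two-sided 0.05, power 0.80 and 200 per phase. The pooled normal formula gives

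n = [1.960·√(2·0.15·0.85) + 0.842·√(0.10·0.90 + 0.20·0.80)]² / 0.10² ≈ 199 per phase,

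with power 0.802 at 200. The stated size reproduces. The calculations below use the 210 per phase to be enrolled, unless noted.

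**Can the per-site tests carry the conclusion?** The power of Fisher's exact test for 10% versus 20%, by full enumeration, is 0.4% at 5 per phase, 7.9% at 21 (210 over ten sites) and 17.5% at the cap of 42. They cannot.

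**Size of the bias.** With two groups of sites,

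shift in pooled difference = (high rate − low rate) × (change in the high-rate group's share of enrollment).

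Site rates are not in the documents. Assume five sites at 5% and five at 15%, averaging the plan's 10%. A/B means A subjects per low-rate site and B per high-rate site in Phase I, swapped in Phase II.

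- 24/18: Phase I 5·(24·0.05 + 18·0.15)/210 = 9.29%; Phase II 10.71%; shift +1.4 points.
- 26/16: 8.81% and 11.19%; shift +2.4 points.
- One low-rate and one high-rate site at 37/5, the other eight at 21: 32·0.10/210 = +1.5 points.

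**Effect on the tests.** 20,000 simulated trials per scenario, ten sites, two-sided 0.05. CMH is the Cochran-Mantel-Haenszel test stratified by site.

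No true effect (false rejection):

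| Mix | Shift (points) | Pooled Fisher | CMH | CMH, continuity-corrected |
|---|---|---|---|---|
| 21/21 (stable) | 0 | 3.2% | 5.1% | 3.4% |
| 24/18 | +1.4 | 5.3% | 4.7% | 3.0% |
| 26/16 | +2.4 | 9.6% | 5.0% | 3.2% |
| One pair 37/5 | +1.5 | 5.5% | 4.8% | not reported |

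True +10 points at every site, shift toward low-rate sites (power):

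| Mix | Pooled estimate (points) | Pooled Fisher | CMH | CMH, continuity-corrected |
|---|---|---|---|---|
| 21/21 (stable) | 10.0 | 79.2% | 83.3% | 79.5% |
| 24/18 | 10 − 1.43 = 8.6 | 65.0% | 82.2% | 78.3% |
| 26/16 | 10 − 2.38 = 7.6 | 54.0% | 81.3% | 76.5% |
| One pair 37/5 | 10 − 1.52 = 8.5 | 64.2% | 78.9% | 74.3% |

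The Mantel-Haenszel risk difference averaged 10.0 points in every row of the second table. With a stable mix the like-for-like comparisons are Fisher 79.2% against corrected CMH 79.5%, and pooled chi-square 82.6% against uncorrected CMH 83.3%. Stratifying is therefore essentially free there, and no power gain is claimed.

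**Range of assumptions.**

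- Equal site rates: no bias at any mix.
- Narrower spread, 8%/12%: shifts of 0.04·30/210 = 0.6 and 0.04·50/210 = 1.0 points at 24/18 and 26/16. False rejection is 3.5% and 4.0%. With the reverse shift, pooled power is 74% and 70%, against 76–82% for CMH.
- Wider spread, 5%/25% (average 15%, above the plan's 10%): 26/16 gives +4.8 points and 22.6% false rejection, against 5.2% for CMH.
- Extreme mix still inside the limits, 37/5 at all ten sites, 5%/15%: +7.6 points and 70% false rejection, against 5% for CMH.
- Random mixes within 5 to 42, 5%/15%: the shift has a 95% range of ±1.4 to ±2.1 points, and false rejection averages 3.9–4.3%.

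**The case against.** The strongest reply is that no error has been shown. The documents give neither the spread of site diagnosis rates nor any reason for site shares to move in step with them. Varying co-morbidities and time to diagnosis are only indirect evidence of different six-month rates. Random changes in mix leave the pooled test below 5%, and even a sorted 24/18 shift gives only 5.3%. Reaching 9.6% needs all five high-rate sites to grow by about 62% and all five low-rate sites to shrink by about 38%. The plan also takes steps toward balance: the desired 45 per center, the cap and the encouraged minimum. Closing a center that enrolled 5 subjects would move the pooled rate by at most about 5/210 × 10 = 0.24 points under the assumed rates. All of this stands, and it is why the point is an optional improvement.

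It does not remove the point. The target of 45 is only desired and the minimum only encouraged, so site shares are not held constant. The power loss under a reverse shift appears already at 24/18, and remains with the narrower 8%/12% spread.

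Stratifying also has a cost when the mix changes a great deal. At 200 per phase and a 35/5 mix at all ten sites, uncorrected CMH power is about 45–50%. If site rates were in fact equal, that loss would buy nothing, since pooled Fisher would keep about 76–77%. If they differ, the pooled test is itself badly biased at such a mix. Finally, stratifying does not address a secular trend between phases or a change in patient selection within sites.

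**Conclusion.** The concern holds, conditionally. The overall primary test does not apply the own-control principle stated in Section 4.4, and nothing else in the plan combines the within-site comparisons. With a stable mix or equal site rates the planned test is unbiased. If shares shift systematically toward or away from high-rate sites, the bias at assumed rates of 5% and 15% is 1.4 to 2.4 points for 24/18 to 26/16. That means false rejection of 5.3–9.6%, or power of 65–54% instead of 79%. The hidden-effect direction is the larger practical risk. These figures rest on assumed site rates and assumed sorted shifts. This is a worthwhile low-cost improvement, not a demonstration that the planned test is invalid.

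**What to change.** In Section 11.1, make the primary overall comparison for Objective #1 site-stratified: a Mantel-Haenszel risk difference with confidence interval, which still estimates the absolute change the endpoint names, and a CMH or exact stratified test. State whether a continuity correction applies. Add site as a term in the overall Poisson regression. Keep the pooled exact test as supportive and the per-site results as description. Report enrollment by site and phase, which Ancillary Objective #4 already requires, so that readers can see whether the mix changed.

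The cost is a change of wording: site and phase are known for every subject, so no new data are needed. There is essentially no power cost with a stable mix. Sites enrolling in only one phase add nothing to the stratified estimate, and very uneven sites add little. The choice should be fixed before outcome data are examined.
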